5.2 Definition of Dose-Limiting Toxicity

Not Applicable

5.3 Dose Expansion Cohorts

Not Applicable

5.4 General Concomitant Medication and Supportive Care Guidelines

Routine supportive care for management of nausea, anorexia, diarrhea, rash and hypertension are allowed. Additional supportive care recommendations are provided below in section 6.

Trametinib is highly bound to plasma proteins (97.3%) and has the potential to interfere with other highly protein-bound drugs. Use caution in patients taking concomitant drugs that are highly protein-bound and have narrow therapeutic ranges. Trametinib is an in vitro inhibitor of CYP 2C8, 2C9, 2C19 and is anticipated to have overall low potential for drug interactions. It is also a weak CYP 2B6 and 3A4 inducer and expected to have little clinical effect on sensitive substrates.

5.5 Duration of Therapy

In the absence of treatment delays due to adverse event(s), treatment may continue for 52 cycles or until one of the following criteria applies:

- Disease progression per RECIST,
- Clinical progression,
- Intercurrent illness that prevents further administration of treatment,

- Unacceptable adverse event(s),
- Patient decides to withdraw from the study
- Pregnancy
 - All women of child bearing potential should be instructed to contact the investigator immediately if they suspect they might be pregnant (e.g., missed or late menstrual period) at any time during study participation.
 - The investigator must immediately notify CTEP in the event of a confirmed pregnancy in a patient participating in the study.
- General or specific changes in the patient's condition render the patient unacceptable for further treatment in the judgment of the investigator.

Patients with clinical progression or disease progression per RECIST who are benefitting from trametinib in reduction of tumor-related symptoms may continue on treatment with trametinib after discussion with the Study PI and CTEP Medical Monitor and approval.

5.6 Duration of Follow Up

Patients will be followed for 24 months after initiation of trametinib unless the patient remains on active treatment beyond 24 months. In that case, follow-up will be continued until 6 months after discontinuation of treatment or until death, whichever occurs first. If the patient discontinues therapy prior to 24 months, follow-up will continue for 6 months after discontinuation or 24 months after initiation of trametinib, whichever is longer. Patients removed from study for unacceptable adverse event(s) will be followed until resolution or stabilization of the adverse event.

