1.2 Secondary Objectives

- Estimate the 6-month and median progression free survival (PFS) rates
- Estimate the 2-year and median overall survival (OS) rates
- Evaluate the safety of trametinib in patients with epithelioid hemangioendothelioma
- Evaluate patient-reported symptoms using NIH PROMIS global health; pain intensity, interference and behavior short form inventories prior to, after 4 weeks and after 6 months (if stable or better disease) of treatment, and on evidence of disease progression

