3. PATIENT SELECTION

3.1 Eligibility Criteria

- 3.1.1 Patients must have measurable disease, defined as at least one lesion that can be accurately measured in at least one dimension (longest diameter to be recorded for non-nodal lesions and short axis for nodal lesions) as ≥ 20 mm (≥ 2 cm) with conventional techniques or as ≥ 10 mm (≥ 1 cm) with spiral CT scan, MRI, or calipers by clinical exam. Baseline imaging must be obtained within 30 days of Day 1 of study. See Section 11 for the evaluation of measurable disease.
- 3.1.2 Patients must have histologically confirmed epithelioid hemangioendothelioma which is metastatic or locally advanced (unresectable), and tumor tissue (paraffin-embedded tissue block or tumor tissue on unstained glass slides) available for fusion FISH analysis at Cleveland Clinic. Patient tumor tissue stored in pathology archives may be used for fusion FISH; a new biopsy is not mandatory.

- 3.1.3 Patients must have evidence of disease progression per RECIST1.1 prior to enrollment or have evidence of cancer-related pain requiring symptom management with narcotic analgesics.
- 3.1.4 Because there is no established standard or approved drug therapy for treatment of EHE, patients previously untreated or treated with drug therapy for EHE are eligible. There is no limit on the number of prior regimens used to be eligible.
- 3.1.5 Age ≥ 15 years. EHE is very unlikely to arise before the age of 15 years.
- 3.1.6 ECOG performance status ≤ 2 (Karnofsky $\geq 60\%$, see Appendix A).
- 3.1.7 Life expectancy of greater than 6 months.
- 3.1.8 Able to swallow orally-administered medication and does not have any clinically significant gastrointestinal abnormalities that may alter absorption such as malabsorption syndrome or major resection of the stomach or small bowel.
- 3.1.9 All prior treatment-related toxicities must be CTCAE v5 grade ≤ 1 (**except alopecia**) at the time of enrollment.
- 3.1.10 Patients must have normal organ and marrow function as defined below within 2 weeks of patient registration (for blood results) and 30 days of registration for LVEF assessment:
 - Absolute neutrophil count (ANC) $\geq 1 \times 10^9/L$
 - Hemoglobin ≥ 9 g/dL, patients may receive transfusion to meet criterion
 - Platelets $\geq 75 \times 10^9/L$
 - Albumin ≥ 2.5 g/dL

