5.7 Criteria for Removal from Study

Patients will be removed from study if they decide to withdraw from the study or die. Patient participation in the study will conclude when they complete study follow-up described in section 5.6. The reason for study removal and the date the patient was removed must be documented in the Case Report Form.

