13. STATISTICAL CONSIDERATIONS

13.1 Study Design/Endpoints

The primary endpoint is the objective response rate using RECIST 1.1. Tumor response assessed by the local site investigator or delegate will be used to assess the objective response rate. Tumor response will be centrally reviewed by [name] but the local site assessment will be used to determine patient treatment and tumor response outcome.

A Simon minimax sampling two-stage design will be used to estimate the objective response rate with a goal of at least 20% of patients to be considered as having preliminary evidence of activity and less than 5% indicating that trametinib is ineffective as a potential EHE treatment. Thirteen patients with EHE will be enrolled in stage I, and if there is at least one objective response as defined by RECIST 1.1, additional patients with EHE will be enrolled until 27 patients with EHE in which *TAZ-CAMTA1* translocation is detected by fusion FISH in archival tumor tissue have been registered and started treatment. The diagnosis of EHE will be determined by the local site, but the presence of *TAZ-CAMTA1* translocation will be determined by the Cleveland Clinic FISH laboratory. If four or more objective tumor responses are documented among 27 patients with *TAZ-CAMTA1* translocation positive EHE, trametinib will be considered to have activity in EHE. With a type 1 error of 5%, this design will have a power of approximately 80% and will have a 51% probability of terminating after the first step if the response rate is 5%. The ORR, 6-month PFS and 2-year OS rates will be calculated along with their 95% confidence intervals. PFS and OS will be estimated by the Kaplan-Meier method.

In stage I enrollment, the presence of *TAZ-CAMTA1* translocation was not detected in 3 tumor samples and in one case there was insufficient tumor tissue available for the analysis. The rate of *TAZ-CAMTA1* translocation negative EHE is higher than the expected rate of less than 10%, and because we anticipate activation of the MAP kinase pathway to occur in tumor with expression of *TAZ-CAMTA1* but not in tumor without the translocation, the protocol is amended to enroll at least 27 patients with EHE containing *TAZ-CAMTA1* translocation.

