Secondary objectives of the 6-month PFS rate, median PFS, and 2-year OS rate will be determined from analyses of patients with *TAZ-CAMTA1* translocation positive EHE. Evaluation of the safety of trametinib, and patient reported symptoms using NIH-PROMIS questionnaires will be determined from analyses of all patients who started treatment with trametinib.

Progression-free survival will be calculated from time of first dose of study medication to occurrence of radiologic tumor progression per RECIST1.1, clinical progression based on treating physician's assessment or death from any cause. Overall survival will be calculated from the time of first dose of study drug to occurrence of death from any cause. Patients who are registered and are determined to be eligible for study treatment but do not start study drug will be replaced. All patients who receive study drug for any period of time will be evaluable for toxicity. The rates of adverse events occurring in at least 5% of subjects and rates of grade 3-5 adverse events will be tabulated by system and term using Common Terminology Criteria of Adverse Events (CTCAE). For dose adjustment schedule see Section 6.1. PROMIS questionnaires will be scored according to recommended standardized system and t-scores generated. A mixed model will be used to analyze change in t-scores over time. Whether or not having evidence of disease progression will be used as a time-dependent variable in the mixed model with adjustment of other potential confounding variables.

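### Median OS is a secondary objective, but survival past month 24 is followed only in patients treated beyond month 18, so a Kaplan-Meier median first reached after month 24 would rest on very few, treatment-selected patients

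*Combined protocol and SAP*

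**What the plan says.** Section 1.2 sets the objective: "Estimate the 2-year and median overall survival (OS) rates".

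Section 13.1 is narrower: "Secondary objectives of the 6-month PFS rate, median PFS, and 2-year OS rate will be determined", from fusion-positive patients. It names a median for PFS and none for OS. Intervals are promised for rates only: "The ORR, 6-month PFS and 2-year OS rates will be calculated along with their 95% confidence intervals". The next sentence says that PFS and OS are both estimated by Kaplan-Meier.

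Section 5.6 sets the observation window: "Patients will be followed for 24 months after initiation of trametinib unless the patient remains on active treatment beyond 24 months". A patient still on drug after month 24 is followed to six months after stopping, or to death. For earlier stoppers, "If the patient discontinues therapy prior to 24 months, follow-up will continue for 6 months after discontinuation or 24 months after initiation of trametinib", and the later of the two dates applies. Section 5.7 then closes the record: "Patient participation in the study will conclude when they complete study follow-up described in section 5.6". Section 5.6 also follows patients removed for adverse events until the event resolves or stabilizes, but that is not survival follow-up.

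**The concern.** The 24-month window fits the 2-year OS rate. It does not fit a median that may fall later, and both OS medians cited in section 2.1 lie beyond month 24.

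After month 24 the Kaplan-Meier curve is carried only by patients who stayed on drug past month 18. A single death can then move it a long way. Suppose 17 of 27 patients are alive at month 24, so the curve stands at 17/27 = 0.63. With three still followed, one death takes it to 0.63 × 2/3 = 0.42, and a median is declared. With four, it falls to 0.63 × 3/4 = 0.47, again below one half.

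In a rare disease such a figure is likely to be set beside the 41 and 32.8 months that the protocol cites. It would come from a small group selected by time on treatment, and the plan does not warn the reader.

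**Working it through.** **The plan's own figures.** The design figures in 13.1 reproduce: with 13 then 27 patients, at least 1 then at least 4 responses, and rates of 5% and 20%, type 1 error is 0.042, power 0.801 and early termination 0.95^13 = 0.513. The plan gives no projection for median OS, so the rest works from its inputs.

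**Follow-up rule.** With T = months on treatment, 5.6 ends follow-up at max(24, T + 6). This exceeds 24 exactly when T > 18.

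**Inputs.**
- n = 27 (13.1).
- PFS medians from 2.1: 4.8 months (retrospective series), 6 months (sorafenib), and 39.1 weeks × 7/30.44 = 9.0 months (bevacizumab, 7 patients).
- OS medians from 2.1: 41 months (retrospective series), and 142.6 weeks × 7/30.44 = 32.8 months (the same 7 patients).
- Assumption: exponential times, with treatment ending at progression, death or 52 cycles (52 × 28 days = 47.8 months).

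**Alive and followed just after month 24.** A simple count is 27 × 0.5^(18/PFS median) × S(24)/S(18), where S(24)/S(18) = 0.5^(6/OS median) = 0.88 to 0.90.
- PFS 4.8: 27 × 0.074 = 2.0, then about 1.8.
- PFS 6: 27 × 0.125 = 3.4, then about 3.0.
- PFS 9: 27 × 0.25 = 6.75, then about 6.0.

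Survivors at month 24 number 27 × 0.5^(24/32.8) = 16.3 or 27 × 0.5^(24/41) = 18.0. Simulation, with OS either linked to progression or not, gives about 1-7 followed of 16-20 alive.

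**Is the median reached by month 24?** That needs at least 14 deaths in 27. The binomial probability is 0.139 (OS 32.8) or 0.036 (OS 41).

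**Simulating the 5.6 rule**, 10,000 trials per scenario. In the linked model, OS = PFS + exponential time after progression; in the other, the two times are independent. Entries are percentages of trials for PFS 4.8 / 6 / 9 months; the last column is the difference of the two before it.

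| OS median, model | Median reached | By month 24 | Only after month 24 |
|---|---|---|---|
| 32.8, linked | 23.8 / 33.8 / 48.9 | 7.9 / 7.0 / 5.6 | 15.9 / 26.8 / 43.3 |
| 32.8, not linked | 26.8 / 36.8 / 59.7 | 14.6 / 14.0 / 14.5 | 12.2 / 22.8 / 45.2 |
| 41, linked | 14.5 / 20.5 / 28.1 | 1.3 / 0.8 / 0.6 | 13.2 / 19.7 / 27.5 |
| 41, not linked | 16.1 / 24.9 / 45.5 | 3.9 / 3.5 / 3.3 | 12.2 / 21.4 / 42.2 |

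Allowing for repeat runs, the median is reached in 13-61% of trials. In 11 of the 12 scenarios a reached median falls after month 24 more often than before it. The scenario-median number at risk at such a late median is 1-3, with a 5th-95th percentile of 1-6. An upper 95% limit exists in at most 1.9% of trials.

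**Selection.** The death rate in months 24-36 among those still followed, relative to all alive at month 24, is 0.41-0.59 in the linked model and 0.96-1.03 in the unlinked one. Kaplan-Meier OS at 24 months stays within 0.2 percentage points of the truth throughout.

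**The case against.** **The median has an estimator.** A reader might infer that the objective has no analysis. That goes too far: 13.1 prescribes Kaplan-Meier for OS, a median can be read whenever the curve reaches one half, and a median that is not reached is a valid result. This stands. The defect is follow-up after month 24 that depends on treatment.

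**The numbers depend on the model.** They are ranges over scenarios, and the time-on-drug inputs come from other drugs. Section 2.1 says that metastatic disease can be stable for years, which suggests a heavier tail. Under assumed alternatives at OS 32.8 months (linked), the typical number at risk rises to 6 with a Weibull PFS (median 9 months, shape 0.6), and to 6 or 7 with exponential PFS medians of 15 or 18 months. With PFS median 6 months, shape 0.6 and no link, the median is reached in 72% (OS 32.8) or 59% (OS 41) of trials. Treatment past progression, where patients "may continue on treatment with trametinib after discussion with the Study PI and CTEP Medical Monitor and approval", raises the typical number at risk to 2-4 if 25% or 50% continue for a mean of six more months (assumed). So no fixed count, and no general claim that the median is usually not reached, is supported. The numbers stay small.

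**OS may be shorter.** Section 3.1 states: "Patients must have evidence of disease progression per RECIST1.1 prior to enrollment or have evidence of cancer-related pain requiring symptom management with narcotic analgesics". A median reached by month 24 would have about 14 at risk and could be read normally. The documents do not settle this. The hepatic series' one-year rate alone implies 12 × ln 2/(−ln 0.733) = 26.8 months, but that means 0.733^5 = 21% alive at five years, against the 30% cited beside it. The five-year rate alone implies 60 × ln 2/(−ln 0.30) = 34.5 months.

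**Bias is not shown.** A reader might infer that a late median is necessarily too high. The linked ratio is partly built in, because that model allows no death before progression; without the link the ratio is about 1. The documents test neither.

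**Conclusion.** The point holds and is minor. Followed as written, the plan can produce a median OS after month 24 that rests on a handful of patients retained because they stayed on drug. With the cited medians and exponential times, a late median occurs in roughly 12-45% of trials and typically has 1-3 at risk. Longer or heavier-tailed treatment raises the counts somewhat without changing the picture. The estimate is biased upward if time on drug goes with survival, and only imprecise if it does not.

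A reader might extend this to survival reporting as a whole. The documents do not support that: every treated patient's window runs to at least 24 months, so the 2-year OS rate is sound, and ORR and its decision rule do not use OS.

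**What to change.** In 13.1, add: 'The secondary Kaplan-Meier OS estimate is reported with numbers at risk and interpreted only to 24 months from first dose; later deaths are listed.'

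Align 1.2 in one of two ways:
- delete 'and median' from the OS objective; or
- keep it, and state that median OS is reported only if reached by month 24, and otherwise as 'not reached by 24 months'.

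The second avoids dropping a pre-specified objective after stage I has enrolled in an open-label trial.

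The cost is a sentence or two of text and, on average, 0.1-1.3 late deaths per trial leaving the secondary estimate (up to 2.1 if treatment past progression is common). No visit or patient contact changes.

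The costlier alternative is to collect survival status for all treated patients, on or off drug, to a common 48 or 60 months. From the binomial probability of at least 14 deaths in 27, the median would be reached in 72-93% of trials at 48 months and 93-99% at 60 months (OS 41 to 32.8 months). It needs an amendment to 5.6, renewed contact with patients whose participation has ended under 5.7, and two to three more years of status checks. It is not needed for this fix.

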5.7 Criteria for Removal from Study

Patients will be removed from study if they decide to withdraw from the study or die. Patient participation in the study will conclude when they complete study follow-up described in section 5.6. The reason for study removal and the date the patient was removed must be documented in the Case Report Form.

6. DOSING DELAYS/DOSE MODIFICATIONS

6.1 Trametinib Dose Modifications

The table below outlines the dose levels to be used for any necessary trametinib dose modifications:

Dose Level	Trametinib Dose/Schedule
0	2 mg once daily
-1	1.5 mg once daily
-2	1 mg once daily

A maximum of two trametinib dose level reductions are allowed. If a third dose level reduction is required, treatment will be permanently discontinued.

If a dose reduction of trametinib is required, but the toxicity resolves and no additional toxicities are seen after two cycles of treatment, the dose of trametinib may be re-escalated but should not exceed 2 mg once a day.

Dose modification and AE guidelines are outlined in the sections below for AEs that are deemed possibly related to trametinib:

- AEs not otherwise specified
- Rash
- Visual changes
- Diarrhea
- Liver chemistry elevation
- Ejection fraction changes
- Hypertension
- Prolonged QTc
- Pneumonitis

6.1.1 Trametinib Dose Modification for Toxicities Not Specified in Subsequent Sections

Trametinib Treatment Modification for Clinically Significant Toxicities Deemed Related to Trametinib (This section is not for specific AEs such as hypertension, rash, ejection fraction changes, pneumonitis, diarrhea, liver chemistry, QTc prolongation, or visual changes. Refer to other sections for these specific AEs).		
CTCAE v5 Grade	Management Guideline	Dose Modification
Grade 1	Monitor as clinically indicated.	Continue trametinib at current dose level.
Grade 2 (tolerable)	Provide supportive care according to institutional standards.	
• Interrupt treatment until resolution to grade 1 or baseline.• Upon resolution, restart treatment at current dose level.
Grade 2 (intolerable) and Grade 3		
• Interrupt treatment until resolution to grade 1 or baseline.• Upon resolution to baseline or grade 1, restart with one level of dose reduction.• If the Grade 3 toxicity recurs, interrupt trametinib; When toxicity resolves to Grade 1 or baseline, restart trametinib reduced by another dose level.
Grade 4		If event resolves to grade 1 or baseline discuss potential continuation of trametinib with Medical Monitor; if continuation of treatment agreed then restart trametinib at dose reduced by one dose level . If event does not resolve, permanently discontinue trametinib.
Trametinib should be discontinued if treatment delay is ≥ 21 days due to toxicities. If the investigator concludes that continued trametinib will benefit a patient, the study chair and CTEP Medical Monitor may be consulted for the possibility of resuming trametinib, provided that toxicities have resolved to baseline or grade 1.		

6.1.2 Trametinib Dose Modification for Rash

Rash is a frequent AE observed in patients receiving trametinib (Investigator's Brochure, 2012a). Recommendations for supportive care and guidelines for dose modifications for rash are based on experience with other MEK inhibitors and EGFR inhibitors (Balagula *et al.*, 2010; Lacouture *et al.*, 2011).

The institutional standards for the management of skin-related AEs can differ from these guidelines. In this case, best clinical judgment should be applied and a consultation with the study chair or the CTEP Medical Monitor may be required.

Guidelines for Supportive Care of Rash	
Type of Care	Action
Prevention/Prophylaxis^a	
 Avoid unnecessary exposure to sunlight. Apply broad-spectrum sunscreen (containing titanium dioxide or zinc oxide) with a skin protection factor (SPF) ≥ 15 at least twice daily. Use thick, alcohol-free emollient cream (e.g., glycerine and cetomacrogol cream) on dry areas of the body at least twice daily. Topical steroids and antibiotics should be applied at least twice daily, starting on Day 1 of study treatment, to body areas such as face, chest, and upper back. Use mild-strength topical steroid (hydrocortisone 1% cream) or topical antibiotic (e.g., clindamycin) or oral antibiotics (e.g., doxycycline 100 mg BID, minocycline 100 mg BID).
Symptomatic Care^b	
 Pruritic lesions: Cool compresses and oral antihistamine therapies. Fissuring lesions: Monsel's solution, silver nitrate, or zinc oxide cream. Desquamation: Thick emollients and mild soap. Paronychia: Antiseptic bath, local potent corticosteroids in addition to antibiotics; if no improvement, consult dermatologist or surgeon. Infected lesions: Appropriate bacterial/fungal culture-driven systemic or topical antibiotics.

^a Rash prophylaxis is recommended for the first 6 weeks of study treatment.

^b Patients who develop rash/skin toxicities should be seen by a qualified physician and should receive evaluation for symptomatic/supportive care management.

Trametinib Dose Modification Guidelines and Management for Rash		
Rash Severity	Management Guideline	Dose Modification
Grade 1	
 Initiate prophylactic and symptomatic treatment measures.¹ Use moderate strength topical steroid.² Reassess after 2 weeks. 	
 Continue trametinib. If rash does not recover to baseline within 2 weeks despite best supportive care, reduce trametinib by one dose level.³

Trametinib Dose Modification Guidelines and Management for Rash		
Rash Severity	Management Guideline	Dose Modification
Grade 2	
 Initiate prophylactic and symptomatic treatment measures.¹ Use moderate strength topical steroid.² Reassess after 2 weeks. 	
 Reduce trametinib by one dose level. If rash recovers to \leq grade 1 within 2 weeks, increase dose to previous dose level. If no recovery to \leq grade 1 within 2 weeks, interrupt trametinib until recovery to \leq grade 1. Restart trametinib at reduced dose level.³
Grade \geq3	
 Use moderate strength topical steroids PLUS oral methylprednisolone dose pack.² Consult dermatologist. 	
 Interrupt trametinib until rash recovers to \leq grade 1. Restart with trametinib reduced by one dose level.^{3,4} If no recovery to \leq grade 2 within 4 weeks, permanently discontinue trametinib.

1. Rash prophylaxis is recommended for the first 6 weeks of study treatment.
 2. Moderate-strength topical steroids: Hydrocortisone 2.5% cream or fluticasone propionate 0.5% cream.
 3. Approval of CTEP Medical Monitor is required to restart study treatment after >4 weeks of interruption.
 4. Trametinib may be escalated to previous dose level if no rash is evident 4 weeks after restarting study treatment.

